Bladder injury, although rare, has serious physical, social and psychological implications.¹³ The injury leads to prolonged operative time, urinary tract infection (UTI), micturition problems and prolonged catheterization.³ A long complicated hospital stay creates an intense feeling of helplessness and anxiety.¹³ Moreover, unrecognized bladder perforation is a leading cause of morbidity due to the development of urinary ascites, peritonitis, and fistula formation.^{14–16}

The adhesions are a major risk factor for bladder injury.¹⁷ Dye test with methylene blue is one of the methods used to identify bladder injury.³ We observed that in women with intact bladder, it made the bladder outline prominent thus improving identification of bladder outline. This observation raised the question of whether improved identification of bladder margins by bladder retro-fill (cysto-inflation) could decrease the occurrence of bladder injury in adhesions of previous C-sections.

In literature, there is insufficient evidence to support the use of cysto-inflation to prevent bladder injury. The routine practice of preoperative insertion of Foleys catheter is based on an old concept that bladder injury may occur by failure to empty the bladder preoperatively.¹⁸ The emptying of bladder improves visualization in the operative field but fails to prevent bladder injury in cases of adhesions.³ Presently, researchers are focussing on prevention of adhesion formation by the use of adhesive barriers and Aloe vera gel but evidence is still needed to prove their effectiveness.^{19,20} The omission of bladder flap formation is also under consideration but there is a lack of adequate evidence to support this method.²¹ The scientists have now started questioning the need for the routine use of an indwelling catheter.^{22–25} The studies indicate that empty bladder is ineffective to avoid bladder injury.^{22–25}

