there while the surgeon holding the tubing will inflate the balloon of the urinary catheter with 10cc distilled water. The theatre attendants will then correct the position of the patient again to straight leg position. The urinary catheter will be kept elevated as long as the patient will be draped with sterilized sheets for operation by the other surgeon. Then, the catheter end near the urinary port will be fixed to the patient sheet in front of the thigh to carry out cystinflation conveniently and attached to the urine bag for drainage.

Adhesiolysis

If adhesions will be encountered during opening the peritoneal cavity or before the separation of bladder flap, the primary surgeons will hold the operation and call the principal surgeon to carry out adhesiolysis and complete the operation. The Principal surgeon will grade the adhesions according to Tulandi's classification and if the woman will fulfil perioperative criteria for adhesions, the Principal surgeon will enrol her in the study as subject and perform randomization into cystoinflation and control groups according to her random number envelope. Adhesiolysis will be performed with the inflated bladder in cystoinflation group, and with the empty bladder in the control group.

Cystoinflation group: The adhesiolysis in cystoinflation group will be performed by bladder retro-fill. Cystoinflation (bladder retrofill) will require normal saline drip and a 60cc bladder wash syringe and an artery clip. In cystoinflation group, the bladder will be retro-filled with 300cc saline by the assigned house officer under strict aseptic measures at the rate of 60cc in one minute. Meanwhile, the principal surgeon will identify the margins of the bladder among adhesions. The catheter will be clamped with an artery clip after filling the bladder with 5 fillings of the syringe. The surgeon will stretch the adhesions by upward traction on the surface of the uterus with a sponge and counter-traction on adhesion with elices forceps or sponge and perform adhesiolysis by sharp dissection with a fine dissecting scissor. The adhesiolysis will be performed until the bladder surface can easily be pushed down. Thereafter, the house officer will attach the urine drainage port of the catheter with the tubing of the urine bag and remove the artery clip to empty the bladder. The surgeon will then push the bladder downward with Doyen's retractor to improve visualization in the surgical field and complete the C-section.

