Control group: The subjects assigned to the control group will undergo no intervention. The Principal surgeon will perform adhesiolysis by the same traction counter-traction method with urinary catheter put on free drainage throughout the C-section.

If there will be a suspicion of bladder injury in either group, it will be confirmed by performing the retrograde dye test with methylene blue and injury will be repaired by the Principal surgeon.

Crossover

There is no possibility of crossover in this study as subjects will be selected during operation and the women who refuse to be included in either group preoperatively will be excluded from the study before group assignment.

Data collection procedure

Data will be collected at the time of admission (baseline), during surgery, on the 3rd postoperative day, at the time of discharge from the hospital and the end of three month follow-up period (for those enrolled in the study). The subjects will be advised to report for any postoperative fever or micturition problem during follow-up. Their visits will be recorded on follow up form by the study team medical officers specifically trained in correctly interpreting the problems of the subjects and filling the outcome form (See [Outcome](#) Form).

Baseline Data

The entry form will include baseline data consisting of demographic features and characteristics of the subjects recruited in the study. The demographic features will include age, gestational age, parity, socioeconomic status, and the number of previous C-sections. The other characteristics will be the score of adhesions and preoperative postmicturition bladder volume. The allotted random number will be entered in entry form of the subject and will be signed and kept in a locked place by study team manager in the theatre. (See [ENTRY FORM](#))

Outcome

Primary outcomes will be the bladder injury rate, the extent of the injury, operative time, blood loss and proportion of subjects receiving blood transfusion.

The bladder injury: The bladder injury will be detected by direct observation during surgery. The suspected bladder injury will be confirmed with the dye test and will be reported as the bladder injury rate and extent of injury.

- A. Bladder injury rate will be recorded as the percentage of subjects with bladder injury in each group.
- B. The extent of the injury will be analyzed by the size, site and depth of injury.

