- IV. **Vesicovaginal or uretro-vaginal Fistula:** In subjects with the complaint of urinary incontinence, the fistula formation i.e. abnormal communication of urinary bladder or ureter with vagina will be ruled out by three swab test and retrograde cystography. The follow up of fistula cases is outside the scope of this study so it will not be included in description or analysis.

C. **Duration of Foleys catheter and hospital stay:** The Foley's catheter will be removed after 24 hours in distension arms of both groups and subjects stay in the hospital for four days. In the bladder injury arms, the catheter will be kept in situ for 7days to give rest to the bladder for the healing of repair of muscularis disruptions, for 10 days in case of repair of perforations smaller than 1cm, and for 14 days for repair of perforations greater than 1cm. After removal of the catheter, the subjects will be kept in the hospital for twelve hours and then discharged if there will have no subjective urinary complaint.

The finding of subjects will be noted on output form by assigned trainees. The participant's first entry on follow up form will be completed on the third postoperative day; second entry will be at the time of discharge from the hospital and last entry at the end of three months postoperative period. In between, they will be advised to visit our team whenever a problem emerges during the postoperative period and their findings will be recorded on the output form. In subjects complaining of urinary incontinence, the fistula formation will be ruled out first by three swab test and then by retrograde cystography. The postoperative visit at the end of 3months will be mandatory. During this visit, all the subjects will be analyzed for postoperative micturition problems and their retrograde cystography will be performed to rule out fistula formation. The subjects with fistula will be referred to the urologist for further management. The last entry at the end of three months will also be mandatory for the inclusion of participant outcome after discharge in results. The participants will be advised to visit the researcher team at the end of 3months period. They will be reminded for their visit on phone call after week if they do not come for follow-up (See [Outcome](#)).

Statistical analysis

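### The primary bladder injury rate counts only injuries seen in theatre by a surgeon who knows the arm; injuries recognised later should count too, with a rule for women who miss follow-up

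*Combined protocol and SAP*

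**What the plan says.** The Outcome section makes the bladder injury rate a primary outcome and fixes how it is found: "The bladder injury will be detected by direct observation during surgery". The next step is conditional: "The suspected bladder injury will be confirmed with the dye test and will be reported as the bladder injury rate and extent of injury". The Control group paragraph gives the same trigger for both arms: "If there will be a suspicion of bladder injury in either group, it will be confirmed by performing the retrograde dye test with methylene blue".

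Bladder fill is what is randomised: "Adhesiolysis will be performed with the inflated bladder in cystoinflation group, and with the empty bladder in the control group". The cystoinflation bladder holds 300cc of saline with the catheter clamped and is emptied once adhesiolysis is done. The control arm is operated on "with urinary catheter put on free drainage throughout the C-section".

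Under Randomisation procedure the theatre nurse discloses the group to the principal surgeon, who then performs adhesiolysis. The Blinding section conceals allocation from surgeons only before the operation. It keeps the follow-up medical officer unaware of the group throughout.

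The Background states that "unrecognized bladder perforation is a leading cause of morbidity", through urinary ascites, peritonitis and fistula. Fistula is a secondary outcome. At the mandatory three-month visit all women are assessed and "their retrograde cystography will be performed to rule out fistula formation". The Outcome Form has a bladder injury entry only under Operative Findings. It has fistula entries at each follow-up and no entry for ascites or peritonitis. Re-surgery appears only as a criterion for a serious adverse event.

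**The concern.** Two features of the definition act together.

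- **Ascertainment closes at the end of the operation.** A woman whose perforation is missed and who later has a fistula is recorded as having no bladder injury in the primary rate. The Background singles out such unrecognised injuries as important.
- **Ascertainment in theatre may not be equal between arms.** A full-depth injury made with fluid in the bladder may be easier to see than one made in a drained bladder, and the threshold for suspicion is set in theatre with the arm known. The first effect would hide control injuries and make cystoinflation look worse. A lower suspicion in the cystoinflation arm would make it look better.

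The Project summary declares the technique effective if its injury proportion is below 50% of control. A ratio rule of this kind is sensitive to unequal detection and, with few events, to single cases.

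**Working it through.** **1. Follow one missed injury through the plan.** A perforation not seen in theatre raises no suspicion, so no dye test is done and the form reads no injury. If it later causes a fistula, that is entered as a secondary outcome. If it leads to re-operation, that is entered as a serious adverse event. If it causes ascites or peritonitis, the Outcome Form has no field for it. No rule carries any of these back to the injury rate.

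**2. Inputs.** The plan gives no detection sensitivity and no control rate for women with dense adhesions, so it has no figure of its own to reproduce here.

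- From the documents: n = 107 per arm (Sample size); success if the observed ratio is below 0.50 (Project summary); 4.49%, the highest injury rate in the Background, which is for sixth caesareans and not specific to dense adhesions.
- Assumed: the sensitivities s_C (control) and s_T (cystoinflation), and the true ratio R.

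**3. Formulas.** Observed ratio = R × s_T / s_C. With equal arms, the chance of meeting the rule is the sum, over all pairs with t < c/2, of Bin(c; 107, 0.0449 × s_C) × Bin(t; 107, 0.0449 × R × s_T).

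**4. Results for R = 0.50.** With full detection the expected counts are 107 × 0.0449 = 4.80 (control) and 107 × 0.0449 × 0.50 = 2.40 (cystoinflation).

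| s_C | s_T | Expected control v cystoinflation | Observed ratio | Chance of meeting rule |
|---|---|---|---|---|
| 100% | 100% | 4.80 v 2.40 | 0.500 | 46% |
| 90% | 95% | 4.32 v 2.28 | 0.50 × 0.95/0.90 = 0.528 | 44% |
| 80% | 95% | 3.84 v 2.28 | 0.50 × 0.95/0.80 = 0.594 | 38% |
| 95% | 80% | 4.56 v 1.92 | 0.50 × 0.80/0.95 = 0.421 | 54% |

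For R = 0.30 the same four rows give 69%, 65%, 60% and 73%. Equal sensitivity in both arms leaves the ratio unchanged.

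**5. Other control rates.** At an assumed 20% control rate and R = 0.50, the chance is 48% with full detection and 31% with 80% v 95%. More events do not remove the effect.

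**6. Attendance.** The Sample size section allows 10% dropout: 0.10 × 107 = 10.7, about 11 women per arm, against about 5 expected control injuries at 4.49%. The Statistical analysis section excludes women who do not return after discharge from the analysis of results. The Secondary Outcomes section makes the three-month entry a condition only for including post-discharge outcomes. A three-month definition cannot be adopted without settling this.

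**The case against.** **The detection mechanism is not in the documents.** This stands. No passage says that a filled bladder reveals a hole or that an empty one hides it. The Background says only that the dye test, itself a retrograde fill, is one way to identify injury. The mechanism is also narrow. Partial-thickness injuries with intact mucosa count too and need not leak, the bladder is emptied after adhesiolysis, and the dye test is open to both arms on suspicion. A reader might infer that the trial is demonstrably biased, against or in favour of cystoinflation. The documents support neither: the leak mechanism and unblinded suspicion can pull in opposite directions, and neither is quantified.

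**Late injuries are not lost to the trial.** This also stands. Fistula is sought in every woman by an officer unaware of allocation, and re-surgery is recorded as a serious adverse event. They are absent only from the primary rate.

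**The illustration rests on chosen sensitivities.** True, and at 90% v 95% the shift is only two percentage points. It shows the possible range in both directions and does not estimate the bias.

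**Counting late injuries does not equalise detection in theatre.** Partly right. A missed injury that heals silently is never recovered, and the outcome comes to depend on attendance. Even so, late ascertainment follows one schedule in both arms and is blind to group, unlike detection in theatre.

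**Conclusion.** The point holds in a limited form. It is established from the text that the primary rate is confined to injuries recognised in theatre, that the operating surgeon knows the arm, and that an injury recognised later does not enter the rate. It is plausible but not established that detection of full-depth injuries during adhesiolysis differs by arm.

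Under the assumptions shown (4.49% control rate, 107 per arm, true ratio 0.50), the chance of meeting the success rule runs from 38% to 54% around 46%. Its position in that range depends wholly on the assumed sensitivities, and the net direction is unknown.

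The definition should be changed because the correction is cheap and uses data already planned. The change is not offered as a remedy for a demonstrated bias.

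**What to change.** 1. **Definition.** Count each woman once as having a bladder injury if it is recognised in theatre or at any time up to three months: postoperative leak, urinary ascites, return to theatre for bladder repair, or fistula on the cystography already scheduled. A fistula after an injury already counted adds nothing. Late events are assessed by the blinded follow-up officer.
2. **Analysis set.** Keep every randomised woman in the injury analysis. A theatre-recognised injury counts whether or not she attends follow-up. A woman without one who misses the three-month visit is analysed on the information available, with a sensitivity analysis for her unknown late status. Amend the exclusion in the Statistical analysis section to match.
3. **Reporting.** Give the theatre-recognised rate as a supporting analysis and tabulate late-recognised injuries by arm.
4. **Form.** Add a field for late-recognised bladder injury, with how and when it was found.
5. **Reconcile.** The Secondary Outcomes section says that follow-up of fistula cases is not described or analysed, yet fistula is an outcome. State that the occurrence of fistula is analysed and what is left out.

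**Cost.** Revised wording and a form field, with no new procedure. The primary outcome becomes final at three months and depends partly on attendance. Injuries that are missed and heal silently remain uncounted.

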Method: We will find out the effectiveness of cystoinflation by conducting a prospective randomized controlled trial in Lady Willingdon Hospital, a university-affiliated teaching hospital in Pakistan, for two years, including a follow-up period of three months. The subjects of the study will be two hundred and fourteen healthy pregnant women with previous operative deliveries which during their C-section, prove to have dense bladder adhesions. The subjects will be randomized into cystoinflation and control groups. Preoperatively, the study team will counsel the women and take informed consent to include them in the study if dense adhesions were found during their C-section. The surgeon will perform adhesiolysis after identifying bladder during retro-fill (with 300cc saline) in the cystoinflation group and without retro-fill in control. The primary outcome will be assessed by bladder injury rate, blood loss and operative time and secondary outcome by postoperative urinary tract infection, micturition problems and fistula formation. Cystoinflation will be considered effective if the proportion of bladder injury in cystoinflation group will be less than 50% of the control.

Discussion: The routine practice of preoperative insertion of urinary catheter fails to prevent bladder injury in multiple C-sections. A few scientists have successfully used cystoinflation technique to prevent bladder injury in pelvic adhesive disease. In this study, we have used cystoinflation in dense adhesions of previous C-sections. The findings of this study may support the previous studies and may serve as a trigger for ongoing research of surgical techniques to prevent iatrogenic bladder injury.

Study protocol: “A controlled study of Cystoinflation to prevent bladder injury in the adhesive disease of multiple caesarean sections”

erb registration: The institutional review board of King Edward Medical University, Pakistan
Reg # 216/RC/KEMU.

Principal Investigator: [name], FCPS; Obstetrics & Gynaecology. Assistant Professor (Obstetrics & Gynaecology), King Edward Medical University /Lady Willingdon Hospital, Lahore, Pakistan

Co-Investigators:

- [name], MS trainee (Obstetrics & Gynaecology), King Edward Medical University /Lady Willingdon Hospital, Lahore, Pakistan
- [name], FCPS trainee (Obstetrics & Gynaecology), King Edward Medical University /Lady Willingdon Hospital, Lahore, Pakistan

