 - i. The size of the injury will be measured in centimetres with a sterilized scale.
 - ii. The site of injury can either be the dome of the bladder, the posterior bladder wall, the trigone or one or both ureters.
 - iii. Depth of injury will be taken as layers involved i.e. either involving muscular layer partly or completely with intact mucosa or full depth injury (perforation).
 - iv.

Operative Time: The staff nurse will record the duration of surgery as time in minutes from incision to closure of the skin.

Blood Loss: The estimated blood loss will be determined by the increase in weight of sponges used during the operation, taking 1 gram equal to 1cc of blood and the number of subjects who received blood transfusion during operation.

Secondary Outcomes

Postoperatively, subjects will be assessed for urinary tract infection (UTI), micturition problems, and fistula formation during the hospital stay and for the next three months. Duration of catheterization and hospital stay will also be recorded. The outcome of each subject will be noted on a Performa by assigned medical officers during the hospital stay and the follow-up period and entered in SPSS20 datasheet.

1-Urinary tract infection (UTI) markers will be more than 10pus cells/hpf in urine or urine showing infectious organisms on culture on the third postoperative day.

- A. **Dysuria** will be expressed by the subject as painful micturition using an 11point Numeric Rating Scale ICCs (.673-.825), $r=.7-.99$. (0 No Pain, 1-3 Mild Pain, 4-6 Moderate Pain, 7-10 Severe Pain).
- B. **Other micturition problems** (feeling of incomplete evacuation, frequency, urgency, urethral and extra-urethral incontinence) will be measured subjectively on Likert scale questionnaire (0-never, 1-rarely, 2-sometimes, and 3-often) and analyzed as a composite variable in spss. Urinary retention will be diagnosed if post-micturition bladder volume is >50cc on ultrasonography on the day of discharge from the hospital.

- I. **Feeling of incomplete evacuation:** It is the feeling created by incomplete emptying of the bladder. The subject will be inquired about the feeling of full bladder accompanying it.
- II. **Urgency** will be diagnosed as a sudden urge to urinate.
- III. **Frequency** Needing to pass urine more than seven times in 24hours.

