We will perform Statistical analysis by using IBM spss statistics 20 (SPSS Inc, Chicago, IL, USA). The characteristics of the subjects will be analyzed as continuous data or ordinal data. Normality of continuous data will be analyzed by the Shapiro Wilk test. The normal baseline data will be compared by T-test, non-normal data by Mann Whitney U test and ordinal data with the chi-square test. The outcome of both groups will be calculated as numbers (percentages) by descriptive statistics. The effect of cysto-inflation on outcome data will be analyzed using regression analysis. The same problem experienced by the same subject will be recorded only once on the spss datasheet. There will be no second entry if the subject presents with the same problem again. The data for any subject who do not come for follow up after discharge will be used and analyzed in study characteristics but will be excluded from the analysis of results. The power of the study for bladder injury will be calculated with statistical software G'Power version 3.1.

Adverse events

The study team will be responsible to record all adverse events and serious adverse events to the subjects of the study, related to or not related to the intervention. The team members will ask open probing questions to enhance the quality of the collected data. An adverse event is

defined as any undesirable experience during follow-up leading to contact with the healthcare system (general practitioner or hospital). If adverse event results in hospitalisation, prolonged inpatient hospital care, result in re-surgery, or if an adverse event is life-threatening, result in death, permanent disability or damage, they will be categorised as serious adverse events. Adverse Events will be recorded in the adverse events reporting register. The study team will report all expected and unexpected adverse events in the study population to the principal investigator in monthly meetings to assess their potential consequences.

Data Management Plan

Documents safety

All the documents, together with the numbered envelopes and the completed forms will be stored in folders that will be kept in the locked research office of the principal investigator with access limited to authorised persons. The study team will ensure that all variables from the completed forms are continuously entered into SPSS 20 datasheet.

Data monitoring

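### Extent of injury is a primary outcome with no value for uninjured women and no stated analysis population, so the natural analysis compares only injured women and can mislead in either direction

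*Combined protocol and SAP*

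**What the plan says.** The Outcome section opens with five primary outcomes: "Primary outcomes will be the bladder injury rate, the extent of the injury, operative time, blood loss and proportion of subjects receiving blood transfusion". The Method paragraph of the Project summary is shorter and leaves extent out: "The primary outcome will be assessed by bladder injury rate, blood loss and operative time".

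Item A of the Outcome section gives the injury rate a clear denominator: "Bladder injury rate will be recorded as the percentage of subjects with bladder injury in each group". Item B, on extent, gives none: "The extent of the injury will be analyzed by the size, site and depth of injury". The sub-items then define each component on an existing injury:

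- Size: "The size of the injury will be measured in centimetres with a sterilized scale".
- Site: a list of bladder locations, plus one or both ureters.
- Depth: "Depth of injury will be taken as layers involved", with two alternatives. Either the muscle is involved (in part or in full) and the mucosa is spared, or the wall is perforated.

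None of the three has a zero or a level for no injury. The Statistical analysis section says that outcomes in both groups will be given as numbers and percentages, and then: "The effect of cysto-inflation on outcome data will be analyzed using regression analysis". It does not say which women enter the analysis of extent. It also removes women who miss follow-up after discharge from the analysis of results.

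**The concern.** Whether a woman is injured is decided after randomisation, and it is what cystoinflation is intended to change. The injured women in one arm are therefore not the randomised counterparts of the injured women in the other. A difference in size or depth between these two groups mixes any effect on severity with the effect on who gets injured. Regression within the injured does not restore the comparison that randomisation provided.

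This matters because extent stands beside the injury rate as a primary outcome. If the technique mainly spared women the small, shallow injuries, those that remained would be larger and deeper on average, and a primary outcome could count against a technique that had only prevented harm. Relabelling extent as secondary would leave the population, and so the problem, unchanged.

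**Working it through.** The plan gives no figure for extent (no expected size, severity mix or power), so there is none to reproduce. The 107 women per arm come from the Sample size section. The rates of 1.17% (fourth section) to 4.49% (sixth) come from the Background. Halving is taken from the Project summary's success criterion of an injury proportion below 50% of control. Everything else below is assumed, as marked.

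**1. How many women would carry the outcome.** Expected injured women in both arms = 107 × p + 107 × p/2 = 107 × p × 1.5.

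- p = 1.17%: 107 × 0.0117 × 1.5 = 1.9.
- p = 4.49%: 107 × 0.0449 × 1.5 = 7.2, split 4.8 control and 2.4 cystoinflation.

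With 5 injured women against 2, the smallest two-sided p-value of an exact rank test on size is 2/C(7,2) = 2/21 = 0.095, even with perfect separation.

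These rates are not for women with dense adhesions. At assumed control rates of 10%, 20% and 30% the expected counts are 10.7 v 5.4, 21.4 v 10.7 and 32.1 v 16.1.

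**2. Direction, by expected counts.** Assume a 20% control rate, with half the injuries muscular only (0.5 cm) and half perforations (2 cm). Control then has 10.7 of each among 107 women. In each case below the technique halves injury overall, to 10.7.

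| Assumed protection | Cystoinflation: muscular / perforation | Perforation share of injured, control v cystoinflation | Mean size in injured, control v cystoinflation | Perforations per randomised woman, control v cystoinflation |
|---|---|---|---|---|
| 80% of muscular, 20% of perforations | 2.14 / 8.56 | 50% v 80% | 1.25 v 1.70 cm | 10% v 8% |
| 50% of each | 5.35 / 5.35 | 50% v 50% | 1.25 v 1.25 cm | 10% v 5% |
| 20% of muscular, 80% of perforations | 8.56 / 2.14 | 50% v 20% | 1.25 v 0.80 cm | 10% v 2% |

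First row: share 8.56/10.7 = 80%; mean size (2.14 × 0.5 + 8.56 × 2)/10.7 = 1.70 cm. Third row: share 2.14/10.7 = 20%; mean size (8.56 × 0.5 + 2.14 × 2)/10.7 = 0.80 cm.

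In the first row the technique reduces both kinds of injury, yet the injured-only comparison goes against it. Over all randomised women, with 0 cm for no injury, mean size is 26.75/107 = 0.25 cm v 18.19/107 = 0.17 cm, the right direction. In the third row the remaining injuries look milder, although no individual injury was made milder. The shares and injured-only means do not depend on the control rate.

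**3. How often a trial of this size would mislead.** Simulation, 3,000 trials per scenario, 107 per arm. Injured-only: Fisher test on perforation share. All women: rank test on none / muscular / perforation.

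| Assumed control rate | First-row protection: injured-only points against technique | of which p < 0.05 (share of trials) | All-women comparison favours technique |
|---|---|---|---|
| 10% | 87% | 9% | 90% |
| 20% | 94% | 28% | 98% |
| 30% | 98% | 45% | 99% |

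Injured-only percentages are among trials with an injury in both arms. Under equal protection the injured-only comparison pointed against the technique in about 48% of trials, and significantly so in 1–2%, so there was no systematic bias.

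**The case against.** The strongest reply is that the plan never restricts extent to injured women. Group outcomes are to be shown as numbers and percentages, and the percentage of each whole group with a perforation would be a proper randomised comparison. That stands: a reader might infer that the plan prescribes an injured-only comparison, and it does not. The restriction is inferred from definitions that leave uninjured women without a value. But percentages do not rescue size in centimetres, and the regression sentence covers outcome data generally without naming a population.

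Second, at the Background rates a false significant result is unlikely. Under the first-row protection it occurred in 0% of simulated trials at 1.17% and about 2% at 4.49%. At 1.17% under halving, both arms have an injury with probability [1 − (1 − 0.0117)^107] × [1 − (1 − 0.00585)^107] = 0.716 × 0.466 = 0.33, so about two-thirds of trials would allow no comparison at all. This also stands. At those rates the analysis is mainly uninformative; the risk of being misled grows with the injury rate, which dense adhesions may raise.

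Third, a reader might infer that the analysis will make a helpful technique look harmful. The documents give no severity mix and no reason to expect mild injuries to be the ones prevented, so the direction is open.

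Fourth, an ordered depth outcome largely repeats the injury-rate comparison. In simulation at a 20% control rate its power was about 50%, against about 48% for Fisher's test on the injury rate. That is a fair cost. The gain is a valid comparison of severity rather than extra power.

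**Conclusion.** The concern holds in this form: a listed primary outcome has no value for most participants and no stated population, and the analysis its definitions lead to is not a randomised comparison. It can err against the technique, err in its favour, or show no systematic bias, depending on which injuries are prevented. The documents do not support the claim that harm will be wrongly shown, nor that an injured-only analysis is written into the plan.

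On size, the outcome would rest on about 2 to 7 women if the Background rates and halving applied. That range assumes a fourth to sixth section. Women at their third section are also eligible (Background rate 0.28%), which would lower the count, while dense adhesions may raise it. The reversal from 50% to 80% perforations, and the 9–45% rate of significant results in the wrong direction, rest on assumed control rates of 10–30% and an assumed severity split. They show what is possible and do not forecast this trial.

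Whether extent is primary at all is unsettled, because the Project summary omits it. Settling that would not cure the population problem.

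**What to change.** In the Outcome and Statistical analysis sections:

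1. Define extent by depth, scored in all randomised women: 0 no injury, 1 muscular layer with intact mucosa, 2 perforation. Split level 1 into partial and complete only if the Outcome Form records the difference.
2. Compare arms with an exact or permutation rank test.
3. State how a ureteric injury is scored, since ureters are a listed site and the depth levels do not cover them.
4. Include every randomised woman. Depth is known at surgery, so the exclusion for missed follow-up should not apply to this outcome.
5. List size and site among injured women descriptively, with no between-arm test.
6. Reconcile the primary outcome lists in the Project summary and the Outcome section.

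The cost is small: no new measurement, revised wording, and coded levels for the Depth row of the Outcome Form, which has none at present. The remaining drawback is the overlap with the injury-rate comparison, so the ordered outcome should not be presented as independent confirmation of it.
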